1.1 Background

Approximately 20% to 30% of patients awaiting cardiac surgery are anaemic. Anaemia is a serious condition increasing the likelihood of requiring a red cell transfusion and is typically associated with increased complications, intensive care, and longer hospital stay after surgery. Iron deficiency is the most common cause of anaemia and it is therefore plausible that administration of preoperative intravenous (IV) iron improve patient outcomes after cardiac surgery. The trial was specifically designed to test the hypothesis that intravenous iron for treatment of anaemia before cardiac surgery (ITACS) will reduce complications and facilitate recovery in anaemic patients awaiting elective surgery. A patient-centred outcome was chosen as the primary endpoint to emphasize the importance given to the patient's experience during their journey to recovery

1.2 Purpose of the analyses

The purpose of this Statistical Analysis Plan (SAP) is to outline the pre-planned analyses to be completed to support the main publication of the ITACS study. Versions of the SAP will be tracked, with a clear distinction between changes before and after start of the statistical analysis.

2 Study design

ITACS is a multicentre, international, double-blind randomised clinical trial comparing the efficacy, safety and cost effectiveness of preoperative intravenous (IV) iron,1000 mg, single dose infusion given 1–26 weeks before the planned date of surgery) with placebo in patients with anaemia before elective cardiac surgery. The trial will incorporate the intervention into normal preoperative surgical pathways for hospital patients. The Trial is registered at ClinicalTrials.gov, Identifier NCT02632760, and the rationale/design article was published in the American Heart Journal in 2021 (doi.org/10.1016/j.ahj.2021.05.008).

2.1 Objectives

Primary objective: To determine whether a single dose of IV iron (ferric carboxymaltose [Ferrinject[®]] or ferric derisomaltose [Monofer[®]] 1000 mg, given to anaemic patients before elective cardiac surgery improves the primary outcome (i.e.

days alive at home up to 90 days (DAH90) after surgery, a validated patient-centred outcome [1]).

Secondary objectives: To assess whether IV iron improves patient recovery because of correction of preoperative iron deficiency anaemia, reduced the need for blood transfusion and risk of complications, manifesting as earlier hospital discharge, lower mortality and reduced readmissions after surgery. We also aim to demonstrate that IV iron is cost-effective in this setting.

Study Hypotheses

Primary: A single dose of IV iron in the weeks before surgery corrects anaemia in patients undergoing elective cardiac surgery, and thereby improves patient recovery and their return to home when compared with placebo.

Secondary (Health Economics): Preoperative administration of IV iron will be 'dominant' when compared with current practice – that is, it will both save money and improve health outcomes.

2.2 Patient population

As indicated in the protocol and reported in our rationale/design publication [2] patients must satisfy all the following inclusion criteria and none of exclusion criteria to be eligible to be randomised to the study

Inclusion criteria

- Adult (\geq 18 years) with anaemia (male or female Hb <130 g/L)
- Expected to undergo elective on-pump or off-pump cardiac surgery
- Able to receive trial drug 1- 26 weeks prior to planned surgery.

_

Exclusion criteria

- Transcatheter aortic valve implantation (TAVI) and other catheter laboratory interventional procedures
- Pregnancy
- Known hypersensitivity to study drug (ferric carboxymaltose, iron isomaltoside, or equivalent) or its excipients
- Previously documented TSAT >50%
- Previously documented vitamin B12 or folate deficiency
- Known or suspected hemoglobinopathy/thalassemia

- Bone marrow disease
- Hemochromatosis
- Renal dialysis
- Erythropoietin or IV iron in the previous 4 weeks

Note: Oral iron (tablets, capsules) therapy is not an exclusion criterion.

2.3 Randomisation

After consent has been obtained, patients are randomly assigned (1:1) to groups via a web-based service using computer-generated code to either receive IV iron or placebo. Group assignment is stratified by site, baseline haemoglobin (< or \geq 100 g/L), and planned surgery (isolated coronary artery or single valve surgery, or combined/other), using a mix of randomly permuted blocks of different sizes.

2.4 Baseline characteristics

Demographics are collected at baseline and include age, sex, weight (kg), weight (cm), ASA, and ethnicity (White/Caucasian, Indian/Pakistan, Asian, Black Other). Various laboratory parameters are also measured i.e. haemoglobin (g/L), creatinine (µmol/L), platelets, CRP (mg/L), Ferritin (ug/L), Transferrin (g/L), Serum Phosphate, (mmol/L), TSAT. A standard measure of health status, EQ–5D [3] is undertaken at baseline and is composed of 5 different domains with 5 questions per domain: mobility, self–care, usual activities, pain/discomfort; anxiety/depression. The EQ5D–VAS score is also collected. The WHODAS 2.0 assessment covering 6 domains of functioning [4] and the MacNew score [5] will also be calculated at baseline (prior to surgery). Finally, information on adverse events (AEs) is collected including AE severity (mild, moderate, severe), AE by system (neurological, cardiovascular, skin, other), SAE/SUSARs at the time of study drug administration.

2.5 Preoperative characteristics

Pre-existing conditions or past events prior to surgery will be recording including smoking history, heart failure, chronic lung disease, diabetes, previous MI. Other standard pre-operative characteristics include 1) prior and concurrent medication i.e. ACE/ARB, β -blockers, Ca Channel blocker, statin, oral iron, IV parenteral iron, red cell transfusion; 2) laboratory parameters e.g. haemoglobin (g/L), haematocrit (L/L), creatinine (µmol/L), CRP (mg/L), ferritin (µg/L), transferrin (g/L), mean corpuscular volume [MCV] (fl), reticulocyte count(x10⁹/L, TSAT (%), platelets, TSH (mIU/L), free thyroxine T4 (pmol/L, alanine transaminase (ALT) (U/L), vitamin B12 (pmol/L), serum folate (nmol/L), GGT (U/L), serum phosphate (mmol/L). Finally, the risk of in-hospital mortality after cardiac surgery as evaluated by the EuroScore II [6] will also be measured preoperatively along with the following quality of life indicators: the functional status (measured by EQ-5D, 5 domains), EQ5D VAS score, the disability status (measured by WHODAS 2.0) and the MacNew score of Heart Disease Health-Related Quality of Life.

2.6 Intraoperative characteristics

The type of surgery will be recorded and divided according to the following categories: CABG only, open valve surgery alone, TAVI alone, other surgery alone, CABG and Valve surgery*, CABG and Other surgery*, Valve and other surgery*, CABG, Valve and Other surgery* (TAVI being excluded for all categories indicated with *). Information on broader categories i.e. CABG, valve repair or replacement, TAVI, other will also be collected along with surgical LV grade (good (EF > 50%), moderate (EF 31–50%), poor (EF 21–30%), very poor (EF < 20%). Other standard characteristics related to surgery are also reported, revision surgery, number of distal anastomosis, total bypass time (min), minimum temperature during bypass (c°), IABP/ECMO/VAD post bypass, lowest haemoglobin concentration during CPB (g/L), inotrope infusion post bypass, cell salvage used during bypass, RBC and units given, platelets and number of units given, fresh frozen plasma (FFP) and number of units given. The total surgical time will be calculated from the first incision until the last suture is inserted.

2.7 Endpoints

2.7.1 Primary endpoint

The primary endpoint, DAH90, is a patient-centred outcome calculated using day and time of surgery as the starting point (Day 0) and calculated thereafter as all days spent at home by the patient until day 90. A few key elements have to be considered to derive this endpoint: 1) a patient who dies within 90 days of surgery is scored as zero irrespective of whether they had spent some of that time at home; 2) in case of hospital readmission after discharge and home return, time spent in hospital due to readmission(s) will be deducted in the DAH90 calculation (up to the limit of 90 days); 3) home is considered to be the patient's normal place of residence or that of a family member, but not a rehabilitation or nursing home facility. This implies that any stay in rehabilitation or nursing home facility within 90 days of surgery will not be classed as "home" in the DAH90 calculation. Examples of DAH90 consistent with this definition are given in the protocol [2

2.7.2 Secondary endpoints

- 1) change in haemoglobin concentration from day of enrolment to day of surgery (preoperative response),
- 2) Correction of iron deficiency state (Δ ferritin, Δ TSat) from treatment to day of surgery
- 3) Change in haemoglobin from day of surgery to 6 weeks post surgery
- 4) Red cell transfusion (any and units) during hospital stay, and post-discharge to 90 days (any).
- 5) Postoperative complications (i.e. MI/stroke/other CVE/infection /thromboembolism) within 30 days of surgery
- 6) 15-item quality of recovery scale on postoperative day 3
- a) Length of stay in hospital (LOS). Hospital stay is calculated from the start (date, time) of surgery until actual hospital discharge or death (in hospital).
 b) ICU stay (hours): ICU stay includes the initial ICU admission and additional time following any ICU readmission up to 30 days after surgery, or death.
- 8) Days alive and at home up to 30 days after surgery (DAH30)
- 9) Disability-free survival, from day of surgery to 6 months after surgery, where disability-free is defined as a WHODAS score <16% at each of 30 days, 90 days and 6 months post surgery.
- 10) Mortality at 30 days, 90 days and 6 months after surgery
- 11) Hospital readmission up to 90 days after surgery
- a) patient-reported quality of life using the MacNew Heart Disease Health-Related Quality of Life Questionnaire (MacNew) up to the day of surgery,
 b) EQ-5D postoperatively at 30 days, 90 days and 6 months after surgery
 c) World Health Organization Disability Assessment Schedule 2.0 (WHODAS) postoperatively at 30 days, 90 days and 6 months after surgery.
- 2.7.3 Safety endpoints (to day 30 post surgery)
 - 1) Anaphylactoid reactions
 - 2) Blood transfusion reactions
 - 3) Cardiovascular events a) MI , b) Stroke)
 - 4) Thromboembolism: as a composite and separated into pulmonary embolism, deep vein thrombosis, Other.
 - 5) Infection a) surgical site, b) deep sternal wound and c) other

6) Adverse events (AE), including the type of AE (neurological, respiratory, gastrointestinal, vascular, renal, skin, musculoskeletal, lymphatic oedema, other [including hypophosphataemia]) and severity (mild, moderate, severe).

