3.5 Preoperative and intraoperative variables

The preoperative and intra-operative data will be summarised and presented by treatment arm using frequencies and percentages for categorical variables, mean and standard deviation for symmetrical continuous variables, or median and quartiles (25th and 75th percentile) for non-symmetrical continuous variables. If variables have more than 5% missing values, we will report the non-missing sample either in the table or in the footnote of the table. No *p*-values will be reported to compare the two arms with the exception of iron-related variables, i.e. Hb, ferritin, transferrin, and mean corpuscular volume

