3.9 Safety endpoints

The type of AEs and AE severity will be tabulated by treatment arm. The number and percentage of patients with at least one AE for each type will be presented. Severity will also be presented accordingly.

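### Hypophosphataemia is pooled into the 'other' adverse-event type, so the SAP plans no separate rate by arm although serum phosphate is listed for collection

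*SAP*

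**What the plan says.** Section 2.7.3 of the SAP defines the safety endpoints under the heading "Safety endpoints (to day 30 post surgery"). Item 6 lists the adverse-event types, and hypophosphataemia appears only in a bracket inside the last of them: "lymphatic oedema, other [including hypophosphataemia". No other laboratory abnormality is named among the safety endpoints.

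Section 3.9 fixes the output: "The type of AEs and AE severity will be tabulated by treatment arm", and "The number and percentage of patients with at least one AE for each type will be presented". Section 3.7 adds risk ratios with 95% CIs for the safety endpoints, but hypophosphataemia is not an endpoint in its own right.

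Serum phosphate is listed twice: in section 2.4 among the baseline laboratory values ("Serum Phosphate, (mmol/L")) and in section 2.5 among the preoperative ones ("serum phosphate (mmol/L")). Section 3.5 summarises preoperative variables by arm, as mean and SD or median and quartiles when continuous, and gives no p-values "with the exception of iron-related variables, i.e. Hb, ferritin, transferrin, and mean corpuscular volume". Phosphate is not on that short list. The SAP states no cut-off for low phosphate and no analysis of its change from baseline.

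**The concern.** The authors thought hypophosphataemia worth naming, and safety is one of the stated purposes of the trial (SAP section 2). Yet the grouping they fix merges it with every unrelated event that fits no other type. A patient with hypophosphataemia and a patient with any other 'other' event add the same single count to the same row. If iron raises the rate, the row reported for that event shows the excess only in diluted form.

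The planned count also depends on a site reporting the event, although an objective measurement is listed in both arms. The continuous summary in section 3.5 does not fill the gap, because a mean with SD or a median with quartiles does not say how many patients were low. If a cut-off is chosen only after the data are seen, any rate reported later is open to the charge of selection.

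**Working it through.** **Reading the sections together.** The SAP has no phosphate figure to reproduce, so the first check is whether any planned output gives a rate by arm.

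| SAP section | What it yields for hypophosphataemia |
|---|---|
| 2.7.3 item 6 | A place inside the type 'other' |
| 3.9 | Number and % with at least one event per type, hence one figure for 'other' |
| 3.7 | Risk ratios for safety endpoints; hypophosphataemia is not a separate one |
| 2.4 and 2.5 | Phosphate listed at baseline and preoperatively |
| 3.5 | Preoperative phosphate by arm, as a continuous summary without a test |

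None gives a count or percentage of hypophosphataemia by arm.

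**How much pooling dilutes.** From the SAP: 1000 patients (2.8), 1:1 allocation (2.3), so about n = 500 per arm; two-sided 5% level (3.1). Assumed, because the SAP gives no rates: hypophosphataemia in p = 6% on iron and 2% on placebo; another 'other' event in a proportion q of each arm, equal in both arms and independent of hypophosphataemia; q = 10%, 20% or 30%.

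Formulas:
- Proportion in the pooled row: 1 − (1 − p)(1 − q).
- SE of log RR: √(1/a − 1/n + 1/b − 1/n), where a and b are the numbers of patients with an event.
- Power, normal approximation: Φ(|p₁ − p₀|√n / √[p₁(1 − p₁) + p₀(1 − p₀)] − 1.96).

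*Separate row.* 30 vs 10 patients, RR = 3.0. SE = √(1/30 + 1/10 − 2/500) = 0.360, so the 95% CI is exp(1.099 ± 1.96 × 0.360) = 1.5 to 6.1. Power is 0.90.

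*Pooled row, q = 20%.* Iron: 1 − 0.94 × 0.80 = 24.8% (124 patients). Placebo: 1 − 0.98 × 0.80 = 21.6% (108 patients). RR = 1.15. SE = √(1/124 + 1/108 − 2/500) = 0.115, 95% CI 0.92 to 1.44.

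| Row | Iron vs placebo | RR | Power |
|---|---|---|---|
| Separate | 6% vs 2% | 3.0 | 0.90 |
| Pooled, q = 10% | 15.4% vs 11.8% | 1.31 | 0.38 |
| Pooled, q = 20% | 24.8% vs 21.6% | 1.15 | 0.22 |
| Pooled, q = 30% | 34.2% vs 31.4% | 1.09 | 0.15 |

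**Other assumed rates.** For 10% vs 5%, a separate row gives RR 2.0 and power 0.85; pooled, the RR is 1.31, 1.17 or 1.10 and power 0.48, 0.30 or 0.21. For a large effect, 15% vs 5%, the RR falls from 3.0 to 1.62, 1.33 or 1.21, and power from about 1.0 to 0.95, 0.81 or 0.63. A large excess can therefore still show in the pooled row, but its size is hidden.

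**Precision of a separate row.** The 95% half-width for one arm is 1.96√[p(1 − p)/500]: 1.2 percentage points at p = 2% and 3.5 at p = 20%.

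**The case against.** The strongest reply is that nothing here is contradictory. The SAP names the event, assigns it to a type and reports type and severity by arm; a separate row is a choice of detail, and the protocol, which is not at hand, may hold definitions and a phosphate cut-off. That stands in part. But how events are grouped for tabulation is the SAP's own business, and the grouping it states obscures the one laboratory event it names.

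Four stronger readings are tempting and are not supported:

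- *The trial cannot state the rate.* A reader might infer this from section 3.9. The SAP only fails to plan a separate estimate; it does not bar listing the named event under 'other', and the listed phosphate values would allow a rate.
- *A harm could surface only in the 'other' row.* Section 3.5 shows preoperative phosphate by arm with its spread. A marked downward shift would be visible there; a difference confined to a small tail, such as 6% vs 2%, might not be. A missing p-value is not a missing summary.
- *Phosphate is known to be measured after the dose.* Section 2.5 does not date the sample. Dosing 1–26 weeks before planned surgery (section 2), and the testing of preoperative iron variables between arms in section 3.5, make a post-dose sample the natural reading, but it is an inference. Completeness of paired samples is unknown.
- *A laboratory proportion would give the incidence after infusion.* One sample at so variable an interval gives prevalence at that visit. It also covers a different period from the safety window to day 30 after surgery.

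The illustrative rates come from no source in the SAP, and the degree of dilution depends on the assumed background rate; hence the ranges.

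**Conclusion.** The point holds as a gap in safety reporting. Followed as written, the SAP yields no separate hypophosphataemia rate by arm, because sections 2.7.3 and 3.9 together pool the event into 'other' and section 3.5 gives phosphate only as a continuous summary. On assumed rates of 6% vs 2% with 500 per arm, pooling reduces a risk ratio of 3.0 to between 1.31 and 1.09 and power from 0.90 to between 0.38 and 0.15. These figures rest on background events that are independent and equally frequent in both arms; they illustrate the dilution and predict nothing about this trial. The primary and secondary efficacy analyses are not affected. The change is worth making before unblinding because it is cheap and uses variables already listed.

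**What to change.** 1. In sections 2.7.3 and 3.9, give reported hypophosphataemia its own row: n/N (%) by arm, with a risk ratio and 95% CI under the binary model of section 3.7, including its provision for few events.
2. From the phosphate data, report by arm the n/N (%) with low preoperative phosphate, using one cut-off for all sites, stated in the SAP before unblinding.
3. Report the between-arm difference in preoperative phosphate from a linear regression adjusted for baseline phosphate, as section 3.7 does for continuous outcomes.
4. Label the laboratory result as prevalence at the preoperative visit. Report the interval from dose to sample and the completeness of paired samples by arm, and note that transient falls may be missed.

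The cost is SAP wording and a few table rows. No new data collection is needed if phosphate was recorded as sections 2.4 and 2.5 list it. Where paired samples are incomplete, the adjusted comparison covers fewer patients, and the report should say how many.

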2.7.4 Heath economics

As explained in the protocol the main question of interest is whether the inclusion of preoperative single dose IV iron in patients with anaemia is a more cost-effective care pathway for elective cardiac surgery than current practice.

The main outcome measure for the economic evaluation will be quality-adjusted life years (QALYs) calculated based on utility weights (estimated by EQ-5D-5L) and life years survived. Other endpoints include: costs related to health care including indexed hospitalization, post-surgical care (medical services, pharmaceutical use, hospital and ambulance service, rehabilitation centre, nursing home, allied health service, etc.). These methods and results will be detailed in a second publication.

2.8 Power and sample size calculation

ITACS is a pragmatic clinical trial aligned to normal hospital pathways. Some preliminary information was available [7] to help calibrate the distribution of DAH90 in the control arm. The endpoint has a left-skewed distribution with a small spike at 0, essentially due to early deaths. Therefore, the sample was determined by simulations (B=10,000 replications) to detect a specific shift in the median DAH90 with power > 90% after accounting for loss to followup and non-compliance. Specifically, DAH90 was obtained by generating first hospital length of stay (LOS) using a lognormal distribution, truncating it at 86 days (allowing for a minimum of 4 days in hospital), and computing DAH90 as 86 minus LOS for 95% of the data on average. The remaining data (5% on average) was generated as 0 to represent a small spike as observed in the original data [7]. A sample size of n=1000 patients was enough to detect a change of 1.45 in the median days with 94% power using a Wilcoxon rank-sum test. This calculation is adjusted for 5% loss to FU and 10% crossover. Power is lower for median regression and depends on the bootstrap method employed to calculate the 95% CI; for instance 84% is obtained using the Markov chain marginal bootstrap [8] available in the R package.

3 Statistical analysis

3.1 Analysis principles

• Analyses will be conducted on a modified intention-to-treat (mITT) basis i.e. patients will be analysed according to the treatment they have been originally assigned to provided data is available (treatment policy estimand).

- All tests are two-sided and the nominal level of type I error will be 5%.
- The primary analysis of the effect of treatment on the primary outcome and key secondary endpoints will be adjusted for the stratification factors of baseline haemoglobin and planned surgery, with region adjusted for as a proxy for site to avoid model convergence issues.
- Subgroup analyses will be carried out irrespective of whether there is a significant treatment effect on the primary outcome.
- No imputation of missing values will be carried out for a percentage of missing values less than 5%. When the proportion of missing is substantial (>5%), a sensitivity analysis for the primary endpoint based on inverse probability weighting will be carried out.
- Analyses will be conducted primarily using Stata or R software.

3.2 Interim analyses

A maximum of 3 analyses included the final analysis are planned with the two interim analyses conducted when 33% and 66% of the data have become available. The O'Brien and Fleming Type I error spending function was used to determine the boundaries at each look. The final last level of significance with 3 looks will consequently be 0.0463.

3.3 Subject Disposition

The flow of study participants will be presented in a Consolidated Standards of Reporting Trials (CONSORT) diagram.

3.4 Demographic and baseline variables

A description of the following baseline characteristics will be presented by treatment group. Discrete variables will be summarised by frequencies and percentages. Percentages will be calculated according to the number of patients for whom data is available. If missing values are \geq 5%, the denominator will be added in a footnote in the corresponding summary table. Continuous variables will be summarised by use of standard measures of central tendency and dispersion, either mean and standard deviation (SD) or median and interquartile range (IQR) as appropriate.

